7.0 Protocol Treatment

Drugs will be administered in accordance with the information on the respective package inserts. Treatment will be given according to the schedule specified in the protocol. The terms “delay,” “modification,” and “omission” are defined as follows:

Delay: A delay indicates dose was postponed or not received when expected.

Modification: Indicates a change in dose level during the current cycle. However, if a modification was issued after the last dose was received in the current cycle, the modification should be reported on the subsequent cycle.

Omission: Indicates a dose was skipped and not made up, or that the drug was discontinued.

Arm A, treatment with regorafenib followed by anti-EGFR therapy (\pm irinotecan).

Arm B, treatment with anti-EGFR therapy (\pm irinotecan) followed by regorafenib.

Treatment on regorafenib will be continued in accordance with Section 7.11 “Planned treatment with regorafenib” until any of the “Criteria for discontinuing treatment with regorafenib” (Section 8.34) is met.

Treatment on Anti-EGFR therapy (\pm irinotecan) will be continued in accordance with Section 8.4, “Combination therapy of Anti-EGFR therapy (cetuximab (Cmab) **OR** panitumumab (Pmab) and irinotecan” until any of the “Criteria for discontinuing treatment including Cmab or Pmab” (Section 8.44) is met.

Patients assigned to Anti-EGFR therapy will receive either cetuximab or panitumumab per treating physician discretion and will be dosed per prescribing guidelines. Patients cannot switch between cetuximab and panitumumab during the course of the study. The use of irinotecan is per treating physician discretion and will be dosed per prescribing guidelines. If treating physician chooses to add irinotecan, irinotecan must be included in treatment starting at cycle 1.

7.1 Treatment Schedule - Use actual weight or estimated dry weight if fluid retention

Agent	Dose	Route	Frequency	ReRx
Regorafenib	80mg daily (Starting dose) See table 7.11	PO	Daily for Days 1-21 of 28 day cycle	Every 28 days
Cetuximab*	500mg/m ²	IV	Days 1, 15	Every 28 days
Panitumumab*	6mg/kg	IV	Days 1, 15	Every 28 Days
Irinotecan	180mg/m ²	IV	Days 1, 15	Every 28 days

* Patients assigned to Anti-EGFR therapy will receive **EITHER** cetuximab **OR** panitumumab, not both

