15.2 Cetuximab (Erbitux®)

- Refer to package insert for complete, up-to-date information.
- 15.21 **Background:** Cetuximab is a recombinant human/mouse chimeric monoclonal antibody which binds specifically to the epidermal growth factor receptor (EGFR, HER1, c-ErbB-1) and competitively inhibits the binding of epidermal growth factor (EGF) and other ligands. Binding to the EGFR blocks phosphorylation and activation of receptor-associated kinases, resulting in inhibition of cell growth, induction of apoptosis, and decreased matrix metalloproteinase and vascular endothelial growth factor production. EGFR signal transduction results in KRAS wild-type activation; cells with KRAS mutations appear to be unaffected by EGFR inhibition.
 - 15.22 **Formulation:** Commercially available for injection 2 mg/mL (50 mL, 100 mL).
 - 15.23 **Preparation, storage, and stability:** Refer to package insert for complete preparation and dispensing instructions. Store intact vials at refrigeration temperature (2 to 8°C 38 to 46°F), do not freeze or shake. Reconstitution is not required. Appropriate dose should be added to empty sterile container; do not shake or dilute. Preparations in infusion containers are stable for up to 12 hours under refrigeration (2 to 8°C 38 to 46°F) and up to 8 hours at room temperature (20 to 36°C or 68 to 77°F).
 - 15.24 **Administration:** Administer via I.V. infusion; loading dose over 2 hours, weekly maintenance dose over 1 hour. Do not administer as I.V. push or bolus. Do not shake or dilute. Premedication with antihistamines is

recommended. The maximum infusion rate is 10 mg/minute. Administer through a low protein-binding 0.22 micrometer in-line filter. Use 0.9% NaCl to flush line at the end of infusion. For biweekly administration (unlabeled frequency and dose), the initial dose was infused over 120 minutes and subsequent doses infused over 60 minutes.

15.25 **Pharmacokinetic information:**

Distribution: $V_d: \sim 2-3 \text{ L/m}^2$

Half-life elimination: $\sim 112 \text{ hours}$ (range: 63-230 hours)

15.26 **Potential Drug Interactions:**

There are no known interactions where it is recommended to avoid concomitant use.

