CAUTION: Infusion reactions may occur during or following cetuximab administration. Most infusion reactions occur with the first infusion of cetuximab, but some patients' first infusion reactions have been reported following subsequent doses (as far out as the 8th dose). The infusion reaction may occur during the infusion, or be delayed until any time after the infusion. A nurse should be present in the immediate treatment area throughout the infusion and observation period. A physician should be in close proximity to the patient treatment area. Should an infusion reaction occur, the patient should be treated according to institutional guidelines. Patient should be instructed to report any delayed reactions to the investigator immediately. Patients who have had severe reactions should not receive further doses of cetuximab.

15.292 Vital signs should be taken prior to, during, post and 1 hour post infusion.

15.293 Patient should be observed for 1 hour following the loading dose and each maintenance dose.

15.294 Premedicate with 50 mg of IV diphenhydramine, or other specific premedications called for in the protocol, prior to each dose.

15.295 Patients should be taught to wear sunscreen and hats and limit sun exposure while receiving treatment.

15.296 Recommend that all infusions be run on a volumetric pump. Infusion rate **MUST NEVER EXCEED 10MG/MINUTE (5 ML/MINUTE)**.

15.297 Monitor CBC and instruct patient to report any signs or symptoms of infection, unusual bruising, or bleeding to the health care team.

15.298 Monitor LFTs.

15.299a Fever and chills may occur. Discuss with MD about premedication with an antipyretic.

15.299b Monitor for signs and symptoms of gastrointestinal side effects, including nausea, constipation, diarrhea, and vomiting. Administer antiemetics and antidiarrheals and/or stool softeners as indicated and evaluate their effectiveness.

15.299c Instruct patient to report rash.

15.299d Hypomagnesemia is a complication of cetuximab therapy. Instruct patients to report any of the following signs or symptoms as these may be signs of the disorder. Neuromuscular: muscle weakness,

muscle cramps, painful swallowing; CNS: Irritability, combativeness, disorientation, psychosis, vertigo, seizures; Cardiac: irregular and/or fast heartbeat. Any or all of the symptoms may or may not be present in the patient with this condition. If patients present with any of these symptoms, inform MD and a magnesium level should be checked.

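### The 60-minute time given in 15.24 for later two-weekly cetuximab infusions breaks the protocol's own 10 mg/min ceiling at full dose once body surface area exceeds 1.2 m².

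*Combined protocol and SAP*

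**What the plan says.** All references are to the combined protocol and SAP.

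- **Dose and schedule (7.1).** Cetuximab is given at 500 mg/m² IV on Days 1 and 15 of a 28-day cycle, so every patient who receives it is on a two-weekly schedule. Section 7.21 gives reduced levels of 400, 300 and 200 mg/m².
- **Infusion time (15.24).** The sentence that opens "For biweekly administration (unlabeled frequency and dose" goes on to report that "the initial dose was infused over 120 minutes and subsequent doses infused over 60 minutes". The only other times in 15.24 are for a loading dose and a weekly maintenance dose, and this trial uses neither.
- **Rate limit (15.24 and 15.296).** Section 15.24 states: "The maximum infusion rate is 10 mg/minute". The nursing guideline in 15.296 says the rate "MUST NEVER EXCEED 10MG/MINUTE (5 ML/MINUTE".
- **Product (15.22 to 15.24).** "Commercially available for injection 2 mg/mL (50 mL, 100 mL" is the formulation, and it must not be diluted.
- **Deferral to labeling (7.0 and 15.2).** Section 7.0 says "Drugs will be administered in accordance with the information on the respective package inserts", and 15.2 opens with "Refer to package insert for complete, up-to-date information".

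**The concern.** Section 15.24 prints a duration and a maximum rate a few sentences apart. At the dose this trial prescribes, both can be met only in very small patients. The 60-minute figure is also the only later-infusion time the protocol offers for its own schedule, so a site looking for a chair time will find that one.

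The limit is a safety limit. Section 15.27 lists severe infusion reactions among cetuximab's boxed warnings. The caution in 15.29 says most reactions come with the first infusion, but that some patients had their first reaction as late as the 8th dose. Those later infusions are the ones affected here. A site that books 60 minutes cannot give the full dose within the limit above 1.2 m², and staff are left to sort out the discrepancy on the day.

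No measured increase in infusion reactions, no bias between arms and no effect on the overall survival comparison is claimed.

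**Working it through.** **Inputs from the protocol**
- Dose: 500 mg/m² (7.1); reduced levels 400, 300 and 200 mg/m² (7.21)
- Infusion times: 120 minutes first, 60 minutes later (15.24)
- Ceiling: 10 mg/min, also stated as 5 mL/min (15.24, 15.296)
- Concentration: 2 mg/mL, undiluted (15.22 to 15.24)

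**Input assumed**
- Body surface area (BSA): not given in the documents. A range of 1.5 to 2.2 m² is used for illustration.

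**Step 1. Reproduce the protocol's own figure.** 10 mg/min ÷ 2 mg/mL = 5 mL/min. The two forms of the ceiling agree.

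**Step 2. Most that can be given in 60 minutes at the ceiling.** 60 × 10 = 600 mg, or 600 ÷ 2 = 300 mL.

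**Step 3. Largest BSA for which 60 minutes fits** (600 ÷ dose per m²)
- Full dose: 600 ÷ 500 = 1.2 m²
- Level -1: 600 ÷ 400 = 1.5 m²
- Level -2: 600 ÷ 300 = 2.0 m²
- Level -3: 600 ÷ 200 = 3.0 m²

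**Step 4. First infusion.** 120 × 10 = 1,200 mg, and 1,200 ÷ 500 = 2.4 m². The 120-minute time fits throughout the assumed range.

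**Step 5. Later full-dose infusions.** Dose = 500 × BSA. Rate over 60 minutes = dose ÷ 60. Shortest permitted time = dose ÷ 10.

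| BSA (m²) | Dose | Volume | Rate over 60 min | Over ceiling | Shortest permitted time |
|---|---|---|---|---|---|
| 1.2 | 600 mg | 300 mL | 10.0 mg/min (5.0 mL/min) | 0% | 60 min |
| 1.5 | 750 mg | 375 mL | 12.5 mg/min (6.25 mL/min) | 25% | 75 min (+15) |
| 1.8 | 900 mg | 450 mL | 15.0 mg/min (7.5 mL/min) | 50% | 90 min (+30) |
| 2.2 | 1,100 mg | 550 mL | 18.3 mg/min (9.17 mL/min) | 83% | 110 min (+50) |

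The 1.2 m² threshold and its reduced-dose counterparts need no outside figure. The percentages and added minutes depend on the assumed BSA range. A lower end of 1.4 m² (700 mg, 11.7 mg/min) would still be 17% over.

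**The case against.** The best reply is that the protocol already shows which text governs. The 60-minute phrase is a past-tense report in a drug-information section, the treatment instructions in 7.0 to 7.2 give no infusion time, and the ceiling is stated as an absolute. On that reading a careful site simply runs the infusion longer. This stands, and it is why the point is not a mandated excess rate. It does not remove the conflict: the figure sits under Administration, it is the only one for this regimen, and it cannot be met within the limit above 1.2 m² at full dose.

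A second reply is that 7.0 and 15.2 defer to the package insert. The insert cannot be seen here, so what it says about infusion time is unknown. But 15.24 itself describes the two-weekly frequency and dose as unlabeled, so the deferral does not clearly supply a time.

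A third is that bedside safeguards limit the harm. Sections 15.291 to 15.294 call for monitoring with resuscitative drugs at hand, vital signs, an hour of observation and premedication before each dose, and 15.296 adds "Recommend that all infusions be run on a volumetric pump". These do lower the stakes. They do not correct the printed time, and a pump set to deliver the volume over 60 minutes would itself exceed the limit.

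It is also fair to say that the practical size rests on an assumed BSA range and on an unknown number of patients. The antibody is the physician's choice (7.0), so the share given cetuximab is not stated.

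**Conclusion.** The concern holds, as a minor inconsistency in safety-relevant administration text. At full dose the 60-minute time and the 10 mg/min ceiling are incompatible above 1.2 m², a result that follows from the protocol's figures alone. The excess of 25% to 83% applies if 60 minutes is followed literally at an assumed 1.5 to 2.2 m². Dose reduction eases the conflict but does not fully remove it: level -1 still conflicts above 1.5 m² and level -2 above 2.0 m². Only later infusions in patients given cetuximab are affected. Sample size, type I error and power are untouched.

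**What to change.** Amend the two-weekly sentence in 15.24 to read along these lines: first infusion over 120 minutes and later infusions over 60 minutes; in either case, (dose in mg ÷ 10) minutes if that is longer, and never faster than 10 mg/min (5 mL/min). Applying the longer-of rule to both infusions also covers a first dose above 2.4 m². No other section needs to change.

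The cost is one sentence by amendment. Relative to 60 minutes, chair time rises by about 15 to 50 minutes per later full-dose infusion at 1.5 to 2.2 m². Sites that already apply the ceiling lose nothing.

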16.0 Statistical Considerations and Methodology

16.1 Overview

This randomized phase II trial is designed to compare the overall survival (OS) in patients with metastatic colorectal cancer, who randomized to regorafenib followed by anti-EGFR therapy (either cetuximab or panitumumab) \pm irinotecan (arm A, R+E) vs. anti-EGFR therapy \pm irinotecan followed by regorafenib (arm B, E+R). Prior studies have shown that the median OS of patients in this disease population who received anti-EGFR follow by regorafenib is around 7.5 months ^{20,32}. It is hypothesized that the sequence of regorafenib followed by anti-EGFR can increase the median OS to 14.5 months. In addition to OS, this trial will also compare the first progression-free survival 1 (PFS1), the second progression-free survival (PFS2), sequential treatment progression-free survival (stPFS), objective response rates (ORR) and adverse event rates between two arms.

This study's original design had no restriction on tumor sidedness. Due to the results of the PARADIGM trial, this study has been amended to reflect treatment patterns where patients will likely receive anti-EGFR therapy as first line therapy. In PARADIGM, the study aimed to test the superiority of panitumumab versus bevacizumab in combination with standard double first-line chemotherapy for patients with newly diagnosed metastatic colon cancer with RAS WT mCRC and left sided tumors. The addition of panitumumab significantly improved overall survival compared to patients who received bevacizumab amongst those with left sided tumors (HR, 0.82; 95.798% CI, 0.68-0.99, p = .031) and the full analysis of all patients (HR, 0.84; 95% CI, 0.72-0.98; p = .030). However, in patients with right sided disease, no improvement in overall survival was observed in patients who received panitumumab (HR 1.09). Given the absence of survival benefit observed in patients with right sided colon cancer, the potential clinical benefit from sequencing therapy remains of interest.

The study has been amended to enrollment of patients with right-sided tumors in Amendment 2. Patients with left-sided tumors who were enrolled prior to Amendment 2 will continue being followed per protocol but their data will not be utilized for the primary endpoint analysis.

Evaluable Population: The Evaluable Population comprises all patients who are eligible, consented, randomized, received any protocol treatment, and have right-sided tumors.

Safety Population: The Safety Population comprises all patients who received any protocol treatment.

- 16.11 **Primary Endpoint:** The primary endpoint is overall survival. The primary objective for this trial is to compare the overall survival (OS) between evaluable patients who were randomized to arm A and arm B. Overall survival is defined as the time from randomization to death from any cause. Patients who are alive at the time of statistical analysis will be censored at the last known alive date.
- 16.12 **Secondary Endpoints:** Each secondary endpoint will be compared between arms. These include first progression free survival (PFS1), second progression free survival two (PFS2), sequential treatment progression free survival (stPFS), objective response rate of initial treatment and sequential treatment, and incidence of adverse events from initial treatment, sequential treatment and whole period.

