1.3 Anti-EGFR antibody-related adverse events

EGFR may control proliferation and differentiation of keratinocytes in normal skin. Inhibition of EGFR results in cessation of proliferation and migration of keratinocytes, leading to apoptosis. In addition, inflammatory cytokines are released, and the entire epidermis may become thin, fragile, vulnerable, and unable to retain moisture¹⁶. Rash acneiform is the most common skin disorder, and usually occurs within 1 to 3 weeks after administration of an anti-EGFR antibody. The most commonly affected area is the upper trunk, including the face, anterior chest, back, and forearm. The severe rash acneiform is often associated with itching and pain. It is replaced by skin dryness and cracking approximately 4 weeks after administration. Paronychia characterized by impaired nail growth and periungual pain may occur 8 weeks or later and be complicated by granulation or abscess in serious cases^{16,17}. Grade 3 or higher skin toxicity has been reported in 9.4% to 16.7% of patients treated with cetuximab⁵⁻⁸, partly contributing to

premature discontinuation of treatment. Another significant adverse drug reaction is severe infusion reaction, with an incidence of less than 5% and interstitial pneumonia (1-2%). In addition, hypomagnesemia, hypokalemia, and hypocalcemia have been reported, requiring monitoring of serum electrolytes before, during, and after treatment and appropriate supplementation as needed.

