7. If baseline history, exam, weight, ECOG PS, and blood pressure were performed ≤ 3 days of C1D1, they do not need to be repeated for C1D1.
8. Receipt of archival tumor tissue is not required for study randomization and initiation of therapy. However, it is mandatory to receive the required tissue ≤ 90 days from randomization. See section 17.0.
9. If screening tests occur ≤ 7 days prior to C1D1, they do not have to be repeated prior to dosing.
10. Kits are required for this collection. Refer to Section 14.0.

11. Patients have the option to complete cfDNA testing at study completion and will be allowed to register with protocol ACCRU-GI-1611. Site will access results through the Guardant Health portal: [REDACTED]. Sites will be notified by Guardant Health via email when results are available in the portal. Refer to Section 13.7. See detailed instructions on the ACCRU website under Manuals and Forms.
12. At the time of disease progression or intolerance from initial treatment, patients will be re-registered (See 6.3) to Sequential Treatment Phase. Tests should be completed after re-registration and prior to dosing of sequential treatment. Patients will then move to the cetuximab or panitumumab ± irinotecan test table (4.2).
13. If the INR/PTT is normal at screening (and subject is not on warfarin) this test will not need to be repeated unless indicated per investigator assessment. If a subject is on warfarin with stable INR/PT at baseline, the INR/PT should be assessed on Day 5 (+/- 3 days). If value is above the therapeutic range, the dose should be modified and the assessment should be repeated weekly until it is stable.

R Research funded.

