6.23 Correlative Research

Mandatory

A mandatory correlative research component is part of this study. The patient will be automatically registered onto this component (see Sections 3.0, 14.0 and 17.0).

Optional

An optional correlative research component is part of this study. There will be an option to select if the patient is to be registered onto this component (see Section 14.0).

- Patient has/has not given permission to give his/her blood sample for research testing.

6.24 At the time of randomization, the following will be recorded:

- Patient has/has not given permission to store and use his/her blood sample(s) for future research to learn, prevent, or treat cancer.
- Patient has/has not given permission to store and use his/her blood sample(s) for future research to learn, prevent, or treat other health problems (for example: diabetes, Alzheimer’s disease, or heart disease).
- Patient has/has not given permission to store and use his/her

tissue sample(s) for future research to learn about, prevent, or treat cancer.

- Patient has/not given permission to store and use his/her tissue sample(s) for future research to learn, prevent, or treat other health problems (for example: diabetes, Alzheimer's disease, or heart disease).
- Patient has/not given permission for ACCRU to give his/her sample(s) to outside researchers.

6.25 Treatment cannot begin prior to randomization and must begin ≤ 14 days after randomization.

6.26 Pretreatment tests/procedures (see Section 4.0) must be completed within the guidelines specified on the test schedule.

6.27 All required baseline symptoms (see Section 10.52) must be documented and graded.

6.28 Treatment on this protocol must commence at an ACCRU institution under the supervision of a medical oncologist.

6.29 a Study drug is available on site.

6.29b Blood draw kit is available on site.

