10.5 Other Required Reporting

10.5.1 Unanticipated Problems Involving Risks to Subjects or Others (UPIRTSOS) in general, include any incident, experience, or outcome that meets all of the following criteria:

1. Unexpected (in terms of nature, severity, or frequency) given (a) the research procedures that are described in the protocol-related documents, such as the IRB-approved research protocol and informed consent document; and (b) the characteristics of the subject population being studied;
2. Related or possibly related to participation in the research (in this guidance document, possibly related means there is a reasonable possibility that the incident, experience, or outcome may have been caused by the procedures involved in the research); and
3. Suggests that the research places subjects or others at a greater risk of harm (including physical, psychological, economic, or social harm) than was previously known or recognized.

Some unanticipated problems involve social or economic harm instead of the physical or psychological harm associated with adverse events. In other cases, unanticipated problems place subjects or others at increased *risk* of harm, but no harm occurs.

Note: If there is no language in the protocol indicating that pregnancy is not considered an adverse experience for this trial, and if the consent form does not indicate that subjects should not get pregnant/impregnate others, then any

pregnancy in a subject/patient or a male patient's partner (spontaneously reported) which occurs during the study or within 120 days of completing the study should be reported as a UPIRTSO.

If the event meets the criteria for an UPIRTSO, submit to your IRB as required by your institutional policies.

10.52 Adverse events to be graded at each evaluation and pretreatment symptoms/conditions to be evaluated at baseline per the CTCAE v5.0 grading unless otherwise stated in the table below:

System Organ Class (SOC)	Adverse event/Symptoms	Baseline	Each evaluation
Gastrointestinal disorders	Diarrhea	# stools per day	X
	Nausea	X	X
	Vomiting	X	X
General Disorders	Fatigue	X	X
	Palmar-plantar erythrodysesthesia syndrome	X	X
Skin and Subcutaneous Tissue Disorders	Rash maculo-papular	X	X
Vascular disorders	Hypertension	X	X
Investigations	Blood bilirubin increased	X	X
	Alanine aminotransferase increased	X	X
	Aspartate aminotransferase increased	X	X

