10.53 Submit via appropriate Academic and Community Cancer Research United (ACCRU) Case Report Forms (i.e., paper or electronic, as applicable) the following AEs experienced by a patient and not specified in Section 10.5:

10.531 Grade 2 AEs deemed *possibly, probably, or definitely* related to the study treatment or procedure.

10.532 Grade 3 and 4 AEs regardless of attribution to the study treatment or procedure.

10.533 Grade 5 AEs (Deaths)

10.5331 Any death within 30 days of the patient's last study treatment or procedure regardless of attribution to the study treatment or procedure.

10.5332 Any death more than 30 days after the patient's last study treatment or procedure that is felt to be at least possibly treatment related must also be submitted as a Grade 5 AE, with a CTCAE type and attribution assigned.

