16.325 Sequential Treatment Objective Response Rate

The objective response rate to sequential treatment is defined as the number of patients who achieve a best response to sequential treatment of complete response or partial response (CR or PR) while on sequential treatment divided by the total number of evaluable patients who initiated sequential treatment. Point estimates and the corresponding 95% confidence intervals for the true success proportions will be calculated.

16.326 Adverse Events

Adverse events by patient will be summarized by frequencies and severity using CTCAE version 5.0. We will also closely monitor adverse events throughout the study.

16.327 Correlative Research

Serial blood collections – prior to cycle 1, every 8 weeks at the time of restaging scans and disease progression will be collected to post-hoc evaluate for plasma biomarkers prognostic or predictive to response and acquired treatment resistance

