18.1 Submission Timetable

Initial Material(s)

CRF	Active-Monitoring Phase (Compliance with Test Schedule Section 4.0)
Institutional Contacts	
On-Study	
On-Study: Prior Surgery ²	
On-Study: Prior Radiation ²	
On-Study: Prior Systemic Therapy ²	
Adverse Events: Baseline	
RECIST Measurements: Initial Treatment (Baseline)	≤2 weeks after randomization
Laboratory Tests & Results: Baseline	
Op and Pathology Reports ¹	
Supporting Documentation: Baseline ³	
Patient Status: Baseline	
Specimen Submission: Blood -Baseline (see Section 14.0)	
Specimen Submission: Tissue-Baseline (see Section 17)	≤2 weeks after randomization
Notice of New Primary ²	
Off Treatment	Submit ≤2 weeks after randomization if withdrawal/refusal occurs prior to beginning protocol therapy
ACCRU Deviation Form ²	Submit only if applicable during all phases of the study

1. Submit Op and Path Reports via the Supporting Documentation: Baseline form.
2. Submit only if applicable.
3. Submit copy of imaging report

Test Schedule Material(s)

CRF	Active-Monitoring Phase (Compliance with Test Schedule Section 4.0)	
	At each evaluation during treatment	At end of treatment
Treatment (Intervention)	X ²	X
Treatment (Intervention): Dose Modifications, Omissions and Delays ³	X	X
Adverse Events: Solicited	X	X
Adverse Events: Other ³	X	X
RECIST Measurements: Initial Treatment ³	X ¹	X ¹
RECIST Measurements: Sequential Treatment (Baseline) ³	X	X
RECIST Measurements: Sequential Treatment ³	X	X
Supporting Documentation ³	X ¹	X
Laboratory Tests and Results	X	X
Specimen Submission: Blood	X (see Section 14.0)	X (see Section 14.0)
Patient Status: Treatment (Intervention)	X	X
End of Initial Treatment		X
Off Treatment		X
Notice of New Primary ³	X	
Consent Withdrawal (choose appropriate form) ³		
• Consent Withdrawal: Optional Specimens	X	X
• Consent Withdrawal: All Follow-Up		
Lost to Follow-Up ³	X	
ACCRU Deviation Form ³	X	

1. Attach a copy of imaging report for each restaging scan and documentation of response or progression in RAVE on the Supporting Documentation Form.
2. Complete at each evaluation during Active Treatment (see Section 4.0).
3. Submit only if applicable.

Follow-up Material(s)

CRF	Event Monitoring Phase ¹				
	q. 3 months until PD	At PD	After PD q.3 mos.	Death	At Each Event Occurrence
Patient Status: Survival and Disease Status Follow-Up/Event Monitoring	X ²	X ²	X	X	At each occurrence
Adverse Events: Late ³					At each occurrence
Supporting Documentation ³					At each occurrence

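### Sequential-phase adverse events have no stated baseline, so first-drug toxicity still present at the switch may be counted in the second drug's table

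*Combined protocol and SAP*

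**What the plan says.** **Endpoint and method.** Goal 2.24 and Section 16.12 compare adverse events between arms. Section 16.12 splits them by phase: "incidence of adverse events from initial treatment, sequential treatment and whole period". The method in 16.326 is that "Adverse events by patient will be summarized by frequencies and severity using CTCAE version 5.0", followed by a general commitment to monitor. It gives no treatment-emergent definition, phase window or sequential-phase baseline, and no rule for an event ongoing at the switch.

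**Grading.** Item 10.52 is headed "Adverse events to be graded at each evaluation and pretreatment symptoms/conditions to be evaluated at baseline per the CTCAE v5.0 grading". Its list includes palmar-plantar erythrodysesthesia (hand-foot reaction), hypertension, bilirubin, ALT and AST. The same list applies on both drugs.

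**Baseline.** Item 6.27, under the randomization procedures, says: "All required baseline symptoms (see Section 10.52) must be documented and graded". In the 18.1 timetable the adverse-event baseline form appears only among the initial materials. Tumor measurements, by contrast, have a second baseline form, "RECIST Measurements: Sequential Treatment (Baseline").

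**The switch.** Section 6.4 allows re-registration after progression or intolerance. It sets maximum intervals (28 days to re-register, 7 more to start) and no minimum. Tables 4.1 and 4.2 both mark an adverse-event assessment at the end of initial treatment. Their footnotes (12 and 11 respectively) state: "Tests should be completed after re-registration and prior to dosing of sequential treatment".

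**The concern.** A plain tabulation by phase counts every event graded during that phase. A patient who leaves regorafenib with hand-foot reaction or raised blood pressure is graded for the same items at the next evaluation on anti-EGFR therapy. Without a rule, that event can appear as an anti-EGFR-phase event. The plan resets the baseline for tumor response at the switch but does not say that it does so for toxicity.

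The sequential-phase table is where a reader would look to see how each drug is tolerated when given second. Section 1.9 gives the different toxicity profiles as one reason for studying the reverse order. Carry-over would mix part of the first drug's profile into the second drug's table, and the first drug differs by arm.

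**Working it through.** The plan states no figure on this point, so there is none to reproduce. The check sets the sections side by side and then sizes one carried-over patient.

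**1. Can an event be ongoing at the switch?** Yes. Section 6.4 permits switching for intolerance. The regorafenib discontinuation criteria in 8.3 include repeated grade 3 hand-foot syndrome and grade 4 hypertension. Section 13.6 lets patients who stop initial treatment for reasons other than progression go on to sequential treatment.

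**2. Would it be graded again on the second drug?** Yes, for the 10.52 items, which are graded at each evaluation whichever drug is being given.

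**3. Would comparison with the entry baseline remove it?** Usually not. Exclusion 3.29o keeps out patients with unresolved toxicity above grade 1 from prior therapy, apart from alopecia and oxaliplatin neurotoxicity up to grade 2. A grade 2 or 3 hand-foot reaction at the switch would normally look new or worse against entry.

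**4. Is the phase boundary fixed for adverse events?** No. PFS2 in 16.322 starts at re-registration, while the switch assessment comes after re-registration and before dosing. If the adverse-event phase borrowed the PFS2 start, events graded before any second-drug dose would fall in the sequential phase.

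**5. Size per patient.** If n patients in an arm start sequential treatment, one carried-over patient who would not otherwise have had the event adds 1/n to that event's reported incidence. The documents do not give n. Assume 15 to 24 of the 26 evaluable patients per arm:

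- n = 15: 1/15 = 6.7 points
- n = 20: 1/20 = 5.0 points
- n = 24: 1/24 = 4.2 points

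Section 16.326 does not say which population the table uses. If it were the Safety Population, with left-sided patients included and all 72 patients treated, split evenly and switching, n could reach 36 and the step would be 1/36 = 2.8 points.

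**6. Size for an assumed carry-over share.** Let p be the second drug's own incidence of the event and c the share entering the phase with it ongoing. Assuming independence, counted incidence = 1 − (1 − p)(1 − c), and the excess is (1 − p)c. The documents give neither value. With p = 2% assumed for hand-foot reaction on anti-EGFR therapy:

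| c (assumed) | Counted incidence | Excess |
|---|---|---|
| 5% | 1 − 0.98 × 0.95 = 6.9% | 4.9 points |
| 10% | 1 − 0.98 × 0.90 = 11.8% | 9.8 points |
| 20% | 1 − 0.98 × 0.80 = 21.6% | 19.6 points |
| 30% | 1 − 0.98 × 0.70 = 31.4% | 29.4 points |

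This is illustration only. The 16.6% in Section 1.5 does not supply c: it is incidence of grade 3 or higher during an earlier trial, not prevalence at a switch in this one.

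**The case against.** **The plan is silent; it does not prescribe misassignment.** This stands. A reader might infer that leftover toxicity will certainly be charged to the second drug. No section says so. The endpoint wording speaks of events from each treatment, which could be read causally, and a pre-dose assessment is scheduled in both arms. The supportable claim is that nothing prevents it.

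**Attribution could sort it out.** A reader might infer that attribution cannot separate the drugs, because item 10.531 asks for "Grade 2 AEs deemed *possibly, probably, or definitely* related to the study treatment or procedure". That item governs which further events are submitted. Section 10.3 defines attribution in terms of the agent(s) or treatment, so drug-level attribution is not ruled out. However, 16.326 makes no use of attribution, and grade 3 and 4 events are submitted regardless of it.

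**Arm B is less clear than Arm A.** This also stands. A reader might infer that anti-EGFR rash reaches the regorafenib table through 10.52. The rash listed there is maculo-papular, whereas Section 1.3 describes acneiform rash, and 10.31 lists the two separately. Nor does late onset help the argument. Section 1.3 says "Paronychia characterized by impaired nail growth and periungual pain may occur 8 weeks or later", but paronychia is not on the 10.52 list, and one that first appears after the switch would still count as new under the fix below.

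**Carry-over may be small.** Partly stands. Week 4 of each regorafenib cycle is off drug, and restaging falls before dosing, so progression found at a scheduled scan nominally follows about a week without regorafenib. Table 8.22b interrupts treatment for the more serious hand-foot reactions, and Section 1.5 reports that events became less frequent after the first course. This applies less to patients who switch because of intolerance.

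**All toxicity present in a phase is a legitimate description.** Agreed, as a statement of what patients experience. The whole-period table already shows the burden of the full sequence. A table labeled by the second treatment should separate what was already there.

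**Conclusion.** The point holds as a gap in the analysis rule, not as a demonstrated bias. Sections 16.12 and 16.326 call for a separate sequential-phase comparison with no baseline for it, and the design makes ongoing toxicity at the switch foreseeable. The clearest exposure is regorafenib hand-foot reaction or hypertension appearing in the Arm A anti-EGFR phase.

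Each carried-over patient adds about 4 to 7 percentage points if 15 to 24 patients per arm start sequential treatment. That range is an assumption, and the total effect cannot be stated because the documents give no carry-over rate.

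The affected result is a descriptive secondary endpoint with no decision rule attached. Overall survival, the initial-phase table and the whole-period table do not change.

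**What to change.** Amend 16.326 to state that:

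1. the adverse-event assessment made after re-registration and before the first sequential dose (4.1 footnote 12; 4.2 footnote 11) is the baseline for the sequential phase;
2. the sequential adverse-event phase starts at the first sequential dose;
3. an event counts in that phase only if it is new or of higher grade than at that assessment;
4. events ongoing at the switch are shown on a separate line;
5. the whole-period table stays as planned.

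**Cost.** A few sentences and a change to the table program. No visit is added and no clinical rule changes. Section 18.1 lists no sequential adverse-event baseline form, so the team should confirm that the switch assessment can be identified in the database; a visit label or form entry may be needed.

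**Downsides.** An event that persists at the same grade because of the second drug will sit on the carry-over line. A delayed first-drug effect that first appears after the switch will still count as new. For events outside the 10.52 list, item 10.53 does not call for grade 1 events, so a rise from grade 1 at the switch cannot be told apart from a new event.
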